	
from the study. (“Dose Determination Visit”; 10-14 days after the Sensitization Visit)
 
The subject will return 72 hours after the application of each dose (0.04, 0.08, 0.12, 0.2%) for an assessment by the PI or co-PI. As described above, the lowest dose will be applied first and assessed. If no reaction, the next lowest dose will be applied, etc, until adequate sensitization is attained. The weakest strength concentration that caused a minimal reaction will be used throughout the study. Once adequate sensitization has been obtained, 0.75-1 g of the treatment drug in that dose will be applied in a thin film that covers the entire scalp.
 
The treatment drug will be applied by the PI, a trained study coordinator, or a staff member of the Clinical Research Unit at the University of Minnesota. Eligible subjects may begin receiving the study drug immediately after enrollment and screening.
 
The estimated duration of the study is 22-24 weeks. See Appendix A for the schedule of visits. There will be a total of 42 scheduled visits, beginning with a screening visit followed by a single sensitizing dose of study drug at baseline (Day -16) and an initial dose determination application of 0.04% DPCP at Day -2. Additional visits could include another sensitization attempt as well as dose determination visits for the .04, 08, 0.12, and 0.2% DPCP.
 
Subjects will undergo twice weekly (+/- 2 days) topical applications of an ointment formulation of DPCP during Weeks 1-18. Application will be done twice per week. The drug application will be performed by a board certified dermatologist for the first two treatment visits (Days 0 and 3; Visits 4 and 5), after which a trained member of the Clinical Research Unit staff or a trained study coordinator will apply the drug twice each week (Weeks 2-18; Visits 6-39). The investigator will attend one treatment visit in the Clinical Research Unit each month to evaluate the extent of hair loss and hair growth (Weeks 4, 8, 12, and 16).
 
Scalp biopsy specimen collection will be performed at baseline (Day -16, Visit 2), 72-96 hours after the first treatment (i.e., challenge) application (Day 2, Visit 5), 72-96 hours after the final application (Week 18 +3d, Visit 39) or during treatment when the study subject is determined to have achieved >=50% hair regrowth.
 
Three scalp biopsy samples will be collected by a board certified dermatologist. When possible, each sample will be taken from a balding area near an area with hair preferably in a non-androgen dependent site of the scalp. One of the three samples will be frozen in OCT for histologic examination and immunohistochemical studies. A second biopsy sample from an adjacent area will be placed in 10% buffered

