2. OBJECTIVES

Primary Objective: To determine the efficacy of DPCP ointment for the treatment of alopecia areata.

Secondary Objectives: 1) To assess the safety of DPCP ointment in alopecia areata subjects.
2) To determine the best starting dose range for future studies

Exploratory Aims: 1) To evaluate the association between cytokine and keratin profiles, Cytomegalovirus UL16 Binding Protein (ULBP) expression and hair regrowth.

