2: DPCP ointment 0.08% will only be applied if participant does not have a strong enough response [defined as skin reaction score 1+] to the 0.04% concentration of DPCP. Thus, this visit will begin with an assessment of the sensitization reaction to the 0.04% dose. If there is not a strong enough response, 0.08% concentration DPCP will be applied to a different area of the inner upper left thigh in the same manner as the 0.005% dose. If the participant is a responder to the 0.04% DPCP, patient will proceed to the challenge visit (visit 4) as described above.

3: DPCP ointment 0.12% will only be applied if participant does not have a strong enough response [defined as skin reaction score 1+] to the 0.08% concentration of DPCP. Thus, this visit will begin with an assessment of the sensitization reaction to the 0.08% dose. If there is not a strong enough response, 0.12% concentration DPCP will be applied to a different area of the inner upper left thigh in the same manner as the 0.08% dose. If the participant is a responder to the 0.08% DPCP, patient will proceed to the challenge visit (visit 4) as described above.

4: DPCP ointment 0.2% will only be applied if participant does not have a strong enough response [defined as skin reaction score 1+] to the 0.12% concentration of DPCP. Thus, this visit will begin with an assessment of the sensitization reaction to the 0.12% dose. If there is not a strong enough response, 0.2% concentration DPCP will be applied to a different area of the inner upper left thigh in the same manner as the 0.12% dose. If the participant is a responder to the 0.2% DPCP, patient will proceed to the challenge visit (visit 4) as described above.

Screening Visit

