ⁱ Drug sensitization procedure

^j Dose determination procedure

^k Pre-treatment labs include TSH, HgB, and Vitamin D

^l Safety monitoring labs include hemoglobin, hematocrit, platelets, WBC, sodium, potassium, chloride, bicarbonate, BUN/urea, total protein, albumin, alkaline phosphate, AST (SGOT), ALT (SGPT), calcium, CRP

^m Women of child bearing potential only

ⁿ See following schedule of events for dose determination visit(s):

Procedure	Visit			
	3 ¹	3 ²	3 ³	3 ⁴
Adverse events	X	X	X	X
Assessment of hair loss	X			
Photographs	X	X	X	X
DPCP ointment – 0.04%	X			
DPCP ointment – 0.08%		X		
DPCP ointment – 0.12%			X	
DPCP ointment – 0.2%				X

1: DPCP ointment 0.04% concentration is the starting concentration for all participants

2: DPCP ointment 0.08% will only be applied if participant does not have a strong enough response to the 0.005% concentration of DPCP. Thus, this visit will begin with an assessment of the sensitization reaction to the 0.005% dose. If there is not a strong enough response, 0.01% concentration DPCP will be applied to a different area of the inner upper left thigh in the same manner as the 0.005% dose. If the participant is a responder to the 0.005% DPCP, patient will proceed to the challenge visit (visit 4) as described above.

3: DPCP ointment 0.12% will only be applied if participant does not have a strong enough response to the 0.01% concentration of DPCP. Thus, this visit will begin with an assessment of the sensitization reaction to the 0.01% dose. If there is not a strong enough response, 0.05% concentration DPCP will be applied to a different area of the inner upper left thigh in the same manner as the 0.01% dose. If the participant is a responder to the 0.01% DPCP, patient will proceed to the challenge visit (visit 4) as described above.

4: DPCP ointment 0.2% will only be applied if participant does not have a strong enough response to the 0.05% concentration of DPCP. Thus, this visit will begin with an assessment of the sensitization reaction to the 0.05% dose. If there is not a strong enough response, 0.1% concentration DPCP will be applied to a different area of the inner upper left thigh in the same manner as the 0.05% dose. If the participant is a responder to the 0.05% DPCP, patient will proceed to the challenge visit (visit 4) as described above.

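### Appendix A, dose-determination footnotes 2 to 4: 15 of 18 concentrations come from a different dose ladder, so these footnotes cannot be followed as written

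*Combined protocol and SAP*

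**What the plan says.** The Study Summary, sections 3, 3.1, 4.1 and 7.3, and Appendix I all use four treatment strengths: 0.04, 0.08, 0.12 and 0.2%. Testing starts at the lowest and moves up one step when the thigh site shows too weak a reaction after 72 hours. The first strength giving a skin reaction score of 1+ becomes the subject's dose for the rest of the study.

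In Appendix A, the dose-determination table assigns these four strengths to visits 3¹ to 3⁴, and footnote 1 agrees: "DPCP ointment 0.04% concentration is the starting concentration for all participants". Footnote 2 then begins: "DPCP ointment 0.08% will only be applied if participant does not have a strong enough response to the 0.005% concentration of DPCP". Later in the same footnote the dose to give is stated as "0.01% concentration DPCP will be applied to a different area of the inner upper left thigh in the same manner as the 0.005% dose". Footnote 3 is built the same way, opening with 0.12% and then using 0.01% and 0.05%. Footnote 4 opens with 0.2% and then says "0.1% concentration DPCP will be applied to a different area of the inner upper left thigh in the same manner as the 0.05% dose".

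The parallel footnotes in section 3.1 are almost entirely on the planned ladder. One stray figure remains in footnote 2: "0.08% concentration DPCP will be applied to a different area of the inner upper left thigh in the same manner as the 0.005% dose".

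**The concern.** The footnotes mix two dose ladders, sometimes within one sentence. Visits 3², 3³ and 3⁴ each end up with two different doses named for them. Under the table, none of the reactions to be assessed (to 0.005, 0.01 and 0.05%) belongs to a dose that has been given. Even on the footnotes' own ladder, 0.005% is never applied, because visit 3¹ uses 0.04%. Footnote 2 therefore has no branch for a subject who does, or does not, react to 0.04%, the one strength every subject receives at this step.

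This is operative text. The Study Summary tells staff "See Appendix A for the schedule of visits", section 7.4 cites the same appendix, and note n of the flowchart leads to this table and its footnotes. The strength chosen here stays with the subject throughout and feeds the second secondary objective: "To determine the best starting dose range for future studies".

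The Appendix A footnotes also omit the 1+ threshold that section 3.1 states, yet they use the word responder. For the arm sensitization site, section 3.1 defines a responder as 2+ or more and classes 1+ as a non-responder. A reader relying on Appendix A alone could carry that rule over and step up a subject who already qualifies.

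**Working it through.** **1. Count of figures.** Each concentration was listed in order and compared with the planned ladder {0.04, 0.08, 0.12, 0.2}.

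| Text | Figures in order (%) | Off ladder |
|---|---|---|
| Appendix A, footnote 2 | 0.08, 0.005, 0.005, 0.01, 0.005, 0.005 | 5 of 6 |
| Appendix A, footnote 3 | 0.12, 0.01, 0.01, 0.05, 0.01, 0.01 | 5 of 6 |
| Appendix A, footnote 4 | 0.2, 0.05, 0.05, 0.1, 0.05, 0.05 | 5 of 6 |
| Section 3.1, footnote 2 | 0.08, 0.04, 0.04, 0.08, 0.005, 0.04 | 1 of 6 |
| Section 3.1, footnote 3 | 0.12, 0.08, 0.08, 0.12, 0.08, 0.08 | 0 of 6 |
| Section 3.1, footnote 4 | 0.2, 0.12, 0.12, 0.2, 0.12, 0.2 | 0 of 6 |

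Appendix A: 5 + 5 + 5 = 15 of 18 (0.005% four times, 0.01% five times, 0.05% five times, 0.1% once). Section 3.1: 1 of 18. Total: 16.

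**2. Size of the discrepancy** (planned divided by written).

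| Visit | Assessed: planned / written | Ratio | Applied: planned / written | Ratio |
|---|---|---|---|---|
| 3² | 0.04 / 0.005 | 8 | 0.08 / 0.01 | 8 |
| 3³ | 0.08 / 0.01 | 8 | 0.12 / 0.05 | 2.4 |
| 3⁴ | 0.12 / 0.05 | 2.4 | 0.2 / 0.1 | 2 |

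Every written dose is lower than the planned one. The ratios size the textual conflict. They do not predict what a subject would receive.

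**3. Could the off-ladder strengths be made?** Section 4.1 has the pharmacy compound 0.08, 0.12 and 0.2% from the supplied 0.4% and 0.04% ointments. The fraction of 0.4% ointment needed for a target t is w = (t − 0.04)/(0.4 − 0.04).

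- 0.005%: −0.035/0.36 = −0.097, not possible
- 0.01%: −0.03/0.36 = −0.083, not possible
- 0.05%: 0.01/0.36 = 0.028, possible
- 0.1%: 0.06/0.36 = 0.167, possible

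Section 7.3 speaks of dilution in the ointment vehicle, and by that route the two lowest strengths could be made. None of the four is a listed study strength.

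**4. Related slips.** In section 3.1, footnote 4 has staff assess the reaction to 0.12% but names only the 0.2% responder as going on to challenge. The pattern of footnotes 2 and 3 calls for 0.12% there. Section 7.4 gives the lowest concentration as 0.045%, which is a typing error for 0.04% and is not in the count.

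**The case against.** The strongest reply is that the intended procedure is easy to recover. The table above the footnotes, footnote 1 and the first words of each footnote name the right dose. The Dose Determination Visit text in section 3.1 gives the full sequence with the 72-hour return, the 1+ criterion and discontinuation after 0.2%, and section 7.3 repeats the order. The off-ladder strengths are not on the pharmacy list, and the Appendix I form has no row for them. The Study Summary has the PI or co-PI assess each reaction, at one site with at most 10 subjects. Confusion is plausible, but misdosing is not shown. The 15 figures are also only four values repeated across six roles.

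Most of this stands, and it keeps the practical risk low. It also means that section 3.1, footnote 4, is an omission in a duplicated note, not a contradiction: a 0.2% responder does proceed, and the 0.12% responder is covered in the visit text. It does not make the Appendix A footnotes usable, since staff must disregard most of what they say and look elsewhere. They are dosing instructions for a drug that section 4.1 describes as a potent sensitizer, and the flowchart sends staff to them.

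**Conclusion.** The point holds and should be fixed. In Appendix A, footnotes 2 to 4, 15 of 18 concentrations are off the planned ladder, with written doses 2 to 8 times lower than planned. One more such figure stands in section 3.1, footnote 2. The footnotes are intact sentences that consistently follow a second ladder (0.005, 0.01, 0.05, 0.1%), so this is not damage from reading the PDF, and they are current text, not a record of changes.

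The conclusion assumes that 0.04, 0.08, 0.12 and 0.2% is the intended ladder. The Study Summary, the body sections, the pharmacy list, Appendix I and Appendix A's own table all support that. The documents give no basis for estimating how often a wrong dose might be given, and none is claimed. The efficacy endpoints, the sample size and the confidence interval widths are unaffected.

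**What to change.** 1. **Appendix A, footnotes 2 to 4.** Replace the assessed doses 0.005, 0.01 and 0.05% with 0.04, 0.08 and 0.12% (four places in each footnote). Replace the applied doses 0.01, 0.05 and 0.1% with 0.08, 0.12 and 0.2% (one place in each). That is 12 + 3 = 15 replacements, leaving 0 of 18 off the ladder. Add the 1+ definition of a sufficient reaction, as in section 3.1.
2. **Section 3.1.** In footnote 2, change 0.005% to 0.04%. In footnote 4, state that a responder to 0.12% proceeds to challenge, and keep the statement that a 0.2% responder also does.
3. **Section 7.4.** Change 0.045% to 0.04%.
4. Notify study staff and the pharmacy of the corrected footnotes.

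The cost is a document correction and a notice, with no extra patients, visits or procedures.

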APPENDIX B: Instructions for Severity OF Alopecia Tool Assessments

Part I: The Severity of Alopecia Tool (SALT)

Overview

The SALT score is a global alopecia areata severity score based on scalp hair loss, as it provides a measure of the percentage of total scalp alopecia. The SALT score is calculated by visually examining four discrete areas of the scalp, measuring the percent of terminal hair loss in each area and then totaling the results. (See below)

The SALT score will be measured to the nearest 1%, following the instructions below, at screening to determine study eligibility and at all following appointments as one measure of the extent of hair loss.

[figure not shown]
Evaluator Requirements

[name] and [name] will be the primary evaluators and will be performing all percentage hair loss assessments for all individual subjects throughout the trial.

Determining SALT score

To determine the SALT score, four main scalp areas are assessed: the left side, the right side, the top and the back. These areas correspond, respectively, to 18%, 18%, 40%, and 24% of the total scalp surface area (see Figure A, “Visual Aid for Determining SALT Score”).

Figure A: Visual Aid for Determining SALT Score

Reference: Figure 1. “Alopecia Areata Investigational Assessment Guidelines –Part II” (Olsen, et. al. 2004).

Determining SALT Score (cont)

The subject's SALT score will be determined as follows:

1. For each of the four main scalp surface areas, the percentage of missing hair will be documented in Row 1.
2. The percentages recorded in Row 1 will be multiplied by the percentages in Row 2 of the same column (Areas as % of Total Scalp Area). The results will be entered in the appropriate columns of Row 3.
3. The four results in Row 3 will be summed to get the percentage hair loss (Row 4).

Sample Worksheet for Determining SALT Score

Row	Parameter	Left	Right	Top	Back
1	Enter % Hair loss for Each Scalp Surface Area				
2	Area as % of Total Scalp Surface	X 0.18	X 0.18	X0.4	X 0.24
3	Multiply Row 1 x Row 2				
4	Total % Hair Loss (Sum the Products from Row 3)				

50% scalp hair regrowth based on SALT score can be expressed as SALT₅₀
75% scalp hair regrowth based on SALT score can be expressed as SALT₂₅

APPENDIX C: Adverse Event Report Log

ADVERSE EVENTS

Has the Subject experienced any Adverse Events since receiving the study treatment?

Yes No

***If yes, complete an SAE CRF.**

**Severity	#Relationship	#Action Taken Regarding Study Drug	^Action Taken to Treat Adverse Event	^^Outcome
1 Mild	1 Definite	1 None – N/A	1 None	1 Continuing
2 Moderate	2 Probable	2 Dose Discontinued	2 Concomitant Medication	2 Resolved
3 Severe	3 Possible		3 Blood Product	3 Lost to Follow-up
4 Life-Threatening	4 Not Related		4 Medical or Surgical Procedure	4 Unknown
			5 Other Intervention	5 Resolved with sequelae
				6 Fatal

Investigator's Signature: _____ Date / / 20 (dd/mmm/yyyy)

APPENDIX D: Serious Adverse Event Report

(Fax completed form to [contact])

Protocol No.	Site No.	Principal Investigator
Date Form Completed	 Initial Report  Follow-Up Report # _____  Final Report	
Reporter Name	Title	Telephone Number

Serious Adverse Event	Onset Date	Resolution Date
		 or Ongoing

Subject ID	Gender	Race	Age	Height	Weight

Study Design					
 Open-Label	 Double-Blind	 Other (specify): Single Blind			
Investigational Drug DPCP (Samcyprone™)	Dose Date	Dose	Route of Administration Topical		
Prescription #					

Criteria for Seriousness (check all that apply)	Action Taken For Event
 Death  Life Threatening  Inpatient Hospitalization *  Prolongation of Existing Hospitalization *  Persistent or Significant Disability / Incapacity  Congenital Anomaly / Birth Defect  Required Intervention to Prevent Permanent Damage  Other (specify) _____	 None  Investigational Drug Dose Discontinued  Required Therapy (specify on page 2)

* Dates of Hospitalization	Admission Date	Discharge Date
-----------------------------------	----------------	----------------

Event Status at Time of This Report	Grade of Event (CTCAE)	Investigator Assessment of Relationship to Investigational Drug	Was Investigational Drug Resumed?
 Recovered/Resolved  Died  Not Recovered/Resolved  Unknown  Recovered/Resolved with Sequelae	 1  4  2  5  3	 Related  Not Related	 Yes  No  N/A

Protocol No.	Site No.	Subject ID
--------------	----------	------------

Known Medications at the Time of the Event

- 1) Exclude those used to treat the event
- 2) A copy of the Concomitant Medication CRF may be attached in place of completing this section

Drug (brand name if known)	Total Daily Dose	Units	Route	Indication	Start Date	Stop Date

Medications Used to Treat the Event

Drug (brand name if known)	Total Daily Dose	Units	Route	Indication	Start Date	Stop Date

Relevant Tests / Laboratory Data

- 1) A copy of the lab reports may be attached in place of completing this section

Clinical Laboratory Test	Normal Range	Value / Date	Value / Date	Value / Date

Relevant Background Information

- 1) Include medical history and demographic data, including pre-existing medical conditions

Protocol No.	Site No.	Subject ID
--------------	----------	------------

Narrative

- 1) Please include any other important information that is not included on the form.
- 2) Supplemental information or supporting documents may be attached.

Investigator's Signature	Date

**Please Email copy of this completed form to Hapten
Pharmaceuticals: [contact]**

APPENDIX E: Demographics & Baseline Assessment

(Visit 1, Date of visit: ____ / ____ / ____)

1. Subject Initials: ___ ___ ___ 2. Subject study number (ID #): ___ ___ ___

3. Date of Birth: / / 4. Gender: Male Female

5. Height? ____ ft. ____ in. / ____ m. ____ cm. 6. Weight? ____ lb. / ____ kg.

7. Blood Pressure: _____ mmHg 8. Pulse _____ bpm

5. If female, urine pregnancy test: Positive Negative

6. Ethnicity: Hispanic/Latino Not Hispanic/Latino

7. Race: Caucasian Black/African American American Indian
 Asian Pacific Islander Multi-racial

Other: _____ Refused

8. Fitzpatrick Skin Type:

- I – Always burns, never tans.
- II – Always burns, rarely tans
- III – Sometimes burns, gradually tans
- IV – Rarely burns, tans well
- V – Rarely burns, always tans
- VI – Never burns, always tans

9. Significant or Recent Medical History:

Condition/Illness/Surgery/Hospitalizations	Condition Status (check if condition is ongoing or resolved)	
	Ongoing	Resolved

Subjects denies any significant medical history, hospitalizations or surgeries

10. Medications Used in Past 6 weeks (Including Current):

APPENDIX F: Treatment History Form

(Visit 1, Date of visit: ____ / ____ / ____)

Of these commonly used therapies for alopecia areata, check all that you use now and have used in the past in the following table:

Therapies:	Current Treatment And Dose	Past Therapies used	Check if Hair Re-growth achieved	Any Side effects of therapy?
None	 _____			
Systemic Steroids "cortisone" Oral (prednisone, medrol) Intramuscular	 _____  _____	 	 	 No  Yes _____  No  Yes _____
Intralesional steroids				 No  Yes
Topical steroids Gel or mousse Lotion, Cream or ointment	 _____  _____	 	 	 No  Yes _____  No  Yes _____
Topical Immunotherapy FK506 (protopic, tacrolimus) Cyclosporine Aldara Elidel Other	 _____  _____  _____  _____  _____	    	    	 No  Yes _____  No  Yes _____
Oral Immunotherapy FK506 (tacrolimus) Cyclosporin Other	 _____  _____  _____	  	  	 No  Yes _____  No  Yes _____  No  Yes _____
Phototherapy NB UVB PUVA – systemic PUVA – topical Excimer laser LLLT	 _____  _____  _____  _____	   	   	 No  Yes _____  No  Yes _____  No  Yes _____  No  Yes _____
Contact Sensitizer DNCB Dinitrochlorobenzene Diphencyprone Squaric acid dibutylester	 _____  _____  _____	  	  	 No  Yes _____  No  Yes _____  No  Yes _____
Retinoids (Vitamin A) Topical _____ Oral _____	 _____  _____	 	 	 No  Yes _____  No  Yes _____
Topical Rogaine/Minoxidil 2% 5%	 _____  _____	 	 	 No  Yes _____  No  Yes _____
Topical Anthraline/Dithrocream	 _____			 No  Yes
Other _____ Other _____ Other _____	 _____  _____  _____	  	  	 No  Yes _____  No  Yes _____  No  Yes _____

APPENDIX G: Physician Assessment of Alopecia

The Physician Assessment of Alopecia includes body hair assessment, nail involvement assessment, duration of current episode of scalp hair loss pattern of scalp hair loss, and SALT scoring assessment.

The proportion of scalp involvement is determined by dividing the scalp into 4 quadrants and estimating the scalp surface that all the alopecic areas would occupy if placed together. The following groups will be used:

 S0 (no scalp hair loss)	 S3 (51-75% hair loss)
 S1 (<=25% hair loss)	 S4 (76-99% hair loss)
 S2 (26-50% hair loss)	 S5 (100% hair loss)

Other areas of alopecia or involvement by alopecia areata may be noted:

B. Extent of Body Hair Loss on the exam today:

 B0 (no body hair loss)	
 B2 (100% body hair loss)	
 B1 (some body hair loss):	
 Eyelashes	 Arms
 Eyebrows	 Trunk
 Beard	 Pubic area
 Axilla	 Legs

N. Degree of Nail Involvement:

 N ₀ (no nail involvement)
 N ₁ (some nail involvement)
 N ₂ (all nails) 20 nail dystrophy

Area: Fingernails Toenails Both

Type: Pitting Onycholysis Onychomycosis Dystrophy

Global assessment: overall improvement. This takes into account extent and density of regrowth by the SALT scoring system. First note regrowth, then categorize by:

 A0 = no change or further loss
 A1 = 1-24% regrowth
 A2 = 25-49% regrowth
 A3 = 50-74% regrowth
 A4 = 75-99% regrowth
 A5 = 100% regrowth

